Day	≤21 days prior to Visit C1D 1	D1	D2 b	D3	D8	D1 5	D1	D2 b	D3 b	D1 c, e	-	30 days after last dose	60 days after last dose	-
Before BNT411 infusion (on infusion days) or on day of visit	E1	X, E3,U a	X, E3,U a	X, U a	X, E3	X	X, E3,U a	X, (E3),U	X	X, E3	X, E1	X, E1	X, E1	X, E1,U
Start of infusion		Ud												
End of infusion (+5 min)		X, E3			X, E3		X, E3			X,E3				
Start of infusion + 1 hour (±5 min)		X					(X)							
Start of infusion + 2.5 hours (±10 min)		X			X		X			X				
Start of infusion + 4 hours (±15 min)		X			X		X			X				
Start of infusion + 6 hours (±15 min)		X, E3 a,			X		X, E3ª			(X)				
Start of infusion + 8 hours (±15 min)		X					(X)							

Note: Time points for blood and urine sampling are to be followed as closely as possible but time deviations no longer than 2 hours will not be reported as protocol deviations as long as the exact times of sampling and dose are known.

E1 – Single ECG assessment.

E3 – Triplicate ECG assessments.

X – Blood sampling.

U – Urine sampling.

UNS - Unscheduled visit.

- (X) Blood sampling will only be performed in potential additional patients enrolled to expand the cohorts for RP2D confirmation.
- (E3) Triplicate ECG assessment will only be performed in potential additional patients enrolled to expand the cohorts for RP2D.

<sup>a Sampling time and sample volume have to be documented.

<sup>b Time window for the Day 2 sample in the dose escalation is 24 hours  $\pm$  1 hour and for Day 3 sample is 48 hours  $\pm$  2 hours after the start of infusion on Day 1.

<sup>c PK and ECG must be obtained in Cycle 3, Cycle 5, Cycle 7, and every 4 cycles thereafter (i.e., Cycles 3, 5, 7, 11, 15, etc.). d 6-hour urine collection after start of BNT411 infusion and total volume collected should be documented.

<sup>e After C3D1, PBMCs (for immune phenotyping and TCR profiling) will no longer be collected. Collection of PMBCs at treatment discontinuation and/or unscheduled visits is only required if the patient discontinues trial treatment prior to C3D1.

Table 1-4: PK (blood and urine) sampling and ECG assessment in Part 1B

Treatment Cycle	Screening			Cycle 1				Cycle 2	2	Cycle 3 - N	Treatment Discontinuation	Safety follow-up 1	Safety follow-up 2	UNS

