Day	≤21 days prior to Visit C1 (D1)	D1	D2	D3 b	D8	D15	D1	D2	D3 b	D2°	-	30 days after last dose	60 days after last dose	-
Before BNT411 infusion (on infusion days) or on day of visit	E1		X,E3, U a	X,E3, U a	X,E3	X		X,E3, U a	X,(E3) ,U a	X,E3	X,E1	X,E1	X,E1	X,E1, U a
Start of infusion			Ud											
End of infusion (+ 5 min)			X,E3		X,E3			X,E3		X,E3				
Start of infusion + 1 hour (± 5 min)			X					(X)						
Start of infusion + 2.5 hours (± 10 min)			X		X			X		X				
Start of infusion + 4 hours (± 15 min)			X		X			X		X				
Start of infusion + 6 hours (± 15 min)			X,E3ª		X			X,E3 a,		(X)				
Start of infusion + 8 hours (± 15 min)			X					(X)						

Note: Time points for blood and urine sampling are to be followed as closely as possible but time deviations no longer than 2 hours will not be reported as protocol deviations as long as the exact times of sampling and dose are known.

E1 – Single electrocardiogram (ECG) assessment.

E3 – Triplicate ECG assessments.

- X Blood sampling
- U Urine sampling

UNS - Unscheduled visit

- (X) Blood sampling will only be performed in potential additional patients enrolled to expand the cohorts for RP2D confirmation.
- (E3) Triplicate ECG assessment will only be performed in potential additional patients enrolled to expand the cohorts for RP2D.
- a Sampling time and sample volume have to be documented.
- b Time window for the Day 3 sample in the dose escalation is 24 hours  $\pm$  1 hour after the start of infusion on Day 2.
- c PK and ECG must be obtained in Cycle 3, Cycle 5, Cycle 7, and every 4 cycles thereafter (i.e., Cycles 3, 5, 7, 11, 15, etc.)
- d 6-hour urine collection after start of BNT411 infusion and total volume collected should be documented.
- e After C3D1, PBMCs (for immune phenotyping and TCR profiling) will no longer be collected. Collection of PMBCs at treatment discontinuation and/or unscheduled visits is only required if the patient discontinues trial treatment prior to C3D1.

**Table 1-5:** Overview of Safety Reporting in Different Countries

Notes: If not specified otherwise, when AE is mentioned, it should also include SAE.

Country	Trial Phase				
	Screening	Treatment Phase	Safety Follow-up Phase	Survival Follow-up Phase	Beyond Trial Closure (if patient is alive and not lost to follow-up)

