# 6.1.1 BNT411

In Part 1A, BNT411 will be administered using a 100 mL intravenous infusion on Days 1, 8 and 15 of each 3-week treatment cycle (21 days) of the first 4 cycles after all required procedures and assessments have been completed. In the following cycles thereafter, BNT411 will be administered every 3 weeks on Day 1 of each 3-week treatment cycle (21 days) after all required procedures and assessments have been completed.

In Part 1B, BNT411 will be administered using a 100 mL intravenous infusion on Days 2, 8 and 15 of each 3-week treatment cycle (21 days) of the first 4 cycles after all required procedures and assessments have been completed. In the following cycles thereafter, BNT411 will be administered every 3 weeks on Day 2 of each 3-week treatment cycle (21 days) after all required procedures and assessments have been completed.

In both Part 1A and Part 1B, patients will be administered BNT411 according to dose levels outlined in Table 4-2. BNT411 will be administered as a body weight-based dosing. A cap on dosing for patients weighing 120 kg and more will be implemented in the proposed clinical trial.

In Part 1B, for combination with atezolizumab and chemotherapy, the administration will be in the following order:

Day 1: Atezolizumab → Carboplatin → Etoposide

Day 2: **BNT411** → Etoposide

Day 3: Etoposide

For each dosing of BNT411 in Cycle 1, patients will remain in the treatment center and be closely monitored for immediate AEs for at least 6 hours. Hospitalization is required for the first 24 hours after the first BNT411 administration in Cycle 1 for clinical observation and PK sampling. Prolongation of the hospitalization beyond 24 hours may be performed at the investigator's discretion if deemed necessary based on potential risks related to the trial treatment and clinical status of the patient. For each subsequent dose of BNT411 in all cycles, patients will be monitored for at least 6 hours.

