8.5.1 Extent of exposure

The following dose exposure variables will be derived and summarized for each treatment (BNT411 in Part 1A also BNT411, atezolizumab, carboplatin, and etoposide in Part 1B). The summaries will be based on patients in the Safety set and will be repeated for DLT evaluation set. The summary for the DLT evaluation set will be restricted to the exposure data from the first cycle (21 days).

- Number of treated cycles.
- Number of BNT411 infusions.

- Number of atezolizumab, carboplatin and etoposide infusions (Part 1B).
- (Actual)Treatment Duration (weeks) defined as follows: (Date of last administration - Date of first administration + Planned Duration) / 7, where the Planned Duration (days) is defined as the planned time between two consecutive administrations. In Part 1A, planned duration for BNT411 is one week for the first four cycles, followed by once every 3 weeks. In Part 1B, planned duration for BNT411 for the first four cycles is 6 days if the patients' last dose was the first dose within any cycle, 7 days if the patients' last dose was the second dose within any cycle and 8 days if the patients' last dose was the third dose in within any cycle. After 4 cycles planned duration for BNT411 is 3 weeks. Planned duration for atezolizumab is every 3 weeks, for carboplatin it is 21 days apart till Cycle 4 and for etoposide planned duration is one day till day 3 of the Cycle 4. Actual treatment duration is calculated for each treatment separately.
- Planned Treatment Duration (weeks) defined as (scheduled date of last administration - scheduled date of first administration + Planned Duration) / 7. The scheduled date of last administration is the date at which the last administration should be given according to the CTP schedule. Planned duration is as above.
- (Actual) Cumulative Dose defined as sum of all administered doses for each trial treatment. BNT411 (μg) for Part 1A and Part 1B and atezolizumab (mg), carboplatin (mg), and etoposide (mg) for Part 1B. Calculated for each treatment separately.
- Planned Cumulative Dose defined as sum of all planned doses, separately, for each trial treatment. BNT411 (μg) for Part 1A and Part 1B and atezolizumab (mg), carboplatin (mg), and etoposide (mg) for Part 1B.
- Dose Intensity is defined as Cumulative Dose for that trial treatment (unit for that trial treatment) / (Actual) Treatment Duration (weeks) for that trial treatment.
- RDI % (using units for BNT411) is defined as follows:

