8.6 Other analyses

8.6.1 Pharmacokinetics

Plasma and urine samples will be collected for measuring concentrations of BNT411 and its metabolites as per the schedule of timing for collection of samples for PK assessments mentioned in Table 1.3 and Table 1.4 of the CTP. For urine sampling, the exact time of sampling and the volume (mL) excreted over each collection interval must be documented. Full pharmacokinetic profiles will be documented in additional patients enrolled to confirm the RP2D. The actual date and time (24-hour clock time) of each sample will be recorded.

Plasma concentrations of BNT411 and its metabolites (if available) will be listed and summarized by cycle, day, nominal time, and cohort for each part of the trial (Part 1A and Part 1B) using descriptive statistics (n, arithmetic mean, SD, coefficient of variation [CV%], geometric mean, geometric CV%, median, minimum, and maximum) for the Full PK analysis set. The geometric CV% will be calculated as the square root of the exponentiated SD of the natural log-transformed data $\text{SQRT}(\exp(sIn^2)-1)$, where appropriate. Mean and individual plots of plasma concentrations will be presented in both the original and semi-logarithmic scales.

All PK parameters will be summarized by cohort for each part of the trial (Part 1A and Part 1B). For $T_{1/2}$, the following descriptive statistics will be calculated, if possible, n, arithmetic mean, median, CV%, SD, minimum and maximum and, for T_{max} , n, median, minimum and max will be calculated. All other PK parameters will be summarized using n, arithmetic mean, SD, CV%, geometric mean, geometric CV%, median, minimum, and maximum.

The following PK parameters will be determined from plasma concentrations of BNT411 after the first dose on Cycle 1 Day 1 (or Cycle 1 Day 2 for Part B):

- AUC_{0-24} : partial AUC from time 0 to 24 hours calculated using the linear-log trapezoidal method.
- AUC_{0-48} : partial AUC from time 0 to 48 hours calculated using the linear-log trapezoidal method.
- $AUC_{0-\text{last}}$: AUC from time 0 to the last measurable time-point calculated using the linear-log trapezoidal method.
- $AUC_{0-\tau}$: AUC from time 0 to the end of the 168-hour dosing interval (τ) calculated using the linear-log trapezoidal method.

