AUC will be computed using the linear-log trapezoidal rule. When necessary, interpolation or λ_z extrapolation may be used to estimate partial AUCs and $AUC_{0-\tau}$. The value of the extrapolated portion of any AUC ($AUC_{\% \text{extrap}}$) will be less than or equal to 20% for the AUC

to be considered well estimated. If this proportion is > 20%, then the values of AUC will be treated with caution. When AUC is calculated and listed, the AUC%_{extrap} will also be listed. Where AUC%_{extrap} >20%, AUC and all related parameters (i.e., CL, V_D) will be presented but excluded from the calculation of summary statistics. All values excluded from the summaries should be flagged in the individual listings with an explanation for the exclusion.

The λ_z will be estimated by log-linear regression of the concentration-time data associated with this phase. The decision as to which data points describe the terminal phase will be reached by inspecting the semi-logarithmic plot of the data, only considering concentrations at time points beyond T_{max}. A minimum of three data points will be used for the estimation of λ_z preferably covering a time span of at least two half-lives. Ideally, the adjusted r² value of the estimated λ_z will be > 0.80. If λ_z is poorly estimated (i.e., if a time span of at least two half-lives is not used or adjusted r² ≤ 0.80), the corresponding T_{1/2} and other parameters derived using λ_z (i.e., AUC_{0-inf}, CL, and V_D) will be flagged in the report and excluded from summaries for PK parameters dependent on λ_z .

In addition to the two plasma PK profiles collected for doses administered on Cycle 1 Day 1 (or Cycle 1 Day 2 for Part B) and Cycle 2 Day 1 (or Cycle 2 Day 2 for Part B), sparse PK samples will be collected at additional times throughout the trial (see CTP Table 1-3 and Table 1-4). Concentrations of BNT411 in pre-dose samples will be considered C_{trough} values provided they are collected between 156 and 180 hours after the start of the prior dose (i.e., 168 ± 12 hours). Concentrations of BNT411 collected within 5 minutes after the end-of-infusion will be considered end-of-infusion concentrations (C_{eoI}). Values of C_{trough} and C_{eoI} will be summarized longitudinally in tabular and graphical format by nominal elapsed time since the start of first infusion of BNT411.

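### With no Part 1B plasma sample between 24 h and the Day 8 pre-dose draw, AUC0-48 is estimated there rather than measured, and the SAP's exclusion rules cut long half-lives about twice as early as in Part 1A.

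*SAP*

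**What the plan says.** SAP 8.6.1 gives one list of plasma parameters "after the first dose on Cycle 1 Day 1 (or Cycle 1 Day 2 for Part B"), so it applies to both parts. The list includes AUC0-48, defined as the "partial AUC from time 0 to 48 hours calculated using the linear-log trapezoidal method", together with AUC0-inf, T1/2, CL and VD. A second list for Cycle 2 drops AUC0-48 and AUC0-inf but keeps T1/2, CL and VD.

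The sampling schedules differ. In Protocol Table 1-3 (Part 1A) the window "for Day 3 sample is 48 hours" ± 2 h after the Day 1 infusion starts, in addition to a 24 h sample on Day 2. In Table 1-4 (Part 1B) the footnote reads "Time window for the Day 3 sample in the dose escalation is 24 hours" ± 1 h, counted from the Day 2 infusion. The next Part 1B blood sample in Cycle 1 is the Day 8 pre-dose draw, in the row labelled "Before BNT411 infusion (on infusion days) or on day of visit". Cycle 2 of Table 1-4 has columns for Days 1, 2 and 3 only.

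Two rules in SAP 8.6.1 then remove values from summaries. The terminal rate constant counts as poorly estimated "if a time span of at least two half-lives is not used" or the adjusted r² is 0.80 or below; T1/2, AUC0-inf, CL and VD are then flagged and left out. Separately, when more than 20% of an AUC is extrapolated, that AUC and the related CL and VD are left out. The same section allows partial AUCs to be interpolated or extrapolated.

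**The concern.** One parameter name, AUC0-48, covers a quantity observed to its end in one part and estimated over its second half in the other.

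The two-half-life rule also selects on the result. A patient is dropped because the estimated half-life is long relative to the sampling span, and the intensive span in Part 1B is about half that in Part 1A. Slow eliminators are lost at a lower threshold in the combination part, which pulls the summarised half-life down and, through the dependent parameters, clearance up. With efficacy analyses withdrawn from Part 1 (SAP 8.4), PK is the only secondary objective still analysed, and a shorter half-life in Part 1B could be taken for an effect of the combination when it comes from the sampling horizon.

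**Working it through.** **Inputs.** Dosing days are 1, 8 and 15 in Part 1A; for Part 1B, Protocol 6.1.1 states: "In Part 1B, BNT411 will be administered using a 100 mL intravenous infusion on Days 2, 8 and 15". The infusion lasts 30 minutes (Protocol 4.4), so if Tmax falls at its end, the first usable point is 1 h. First-dose samples then follow at 2.5, 4, 6, 8 and 24 h, plus 48 h in Part 1A (Tables 1-3 and 1-4). In Cycle 2 the 1 h and 8 h samples are drawn only in extra patients added for RP2D confirmation, so other patients start at 2.5 h. The half-life and LLOQ are not given and are treated as unknown.

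**Step 1: nominal times.** Part 1A Day 3 is (3 − 1) × 24 = 48 h; Part 1B Day 3 is (3 − 2) × 24 = 24 h. Both agree with the table footnotes. Part 1B Day 8 is (8 − 2) × 24 = 144 h, consistent with the six-day gap in SAP 8.5.1 ("In Part 1B, planned duration for BNT411 for the first four cycles is 6 days if the" last dose was the first of a cycle).

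**Step 2: largest half-life that survives the two-half-life rule** = (last sample − first sample after Tmax) / 2.

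| Profile | Part 1A | Part 1B |
|---|---|---|
| Cycle 1, intensive samples | (48 − 1)/2 = 23.5 h | (24 − 1)/2 = 11.5 h |
| Cycle 2, no 1 h sample | (48 − 2.5)/2 = 22.75 h | (24 − 2.5)/2 = 10.75 h |
| Cycle 1, Day 8 pre-dose used | (168 − 1)/2 = 83.5 h | (144 − 1)/2 = 71.5 h |

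The first two rows are upper limits. A fit to the 6, 8 and 24 h points alone gives (24 − 6)/2 = 9 h in Part 1B.

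**Step 3: can the Day 8 value help?** Under mono-exponential decline C144/C24 = 2^(−120/T), where T is the half-life. This is 0.07% at 11.5 h, 1.6% at 20 h and 3.1% at 24 h. Half-lives just above 11.5 h would probably still be lost, while much longer ones might be kept. The LLOQ decides.

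**Step 4: share of AUC0-48 lying after 24 h** = x/(1 + x), with x = 2^(−24/T). This is 1.5% at 4 h, 11% at 8 h, 20% at 12 h and 33% at 24 h.

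**Step 5: the 20% rule for first-dose AUC0-inf.** The extrapolated share after the last sample at time t is 2^(−t/T). Setting it to 0.20 gives T = t × ln 2 / ln 5, which is 10.3 h for t = 24 and 20.7 h for t = 48.

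**Step 6: patients excluded by the two-half-life rule**, assuming a lognormal half-life, fits starting at 1 h, a quantifiable last intensive sample and no usable Day 8 value. With σ = √ln(1 + CV²), the excluded share is 1 − Φ(ln(ceiling/GM)/σ).

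- GM 6 h, CV 30% (σ = 0.294): Part 1B ln(11.5/6)/σ = 2.22, so 1.3%.
- GM 8 h, CV 30%: Part 1B ln(11.5/8)/σ = 1.24, so 11%; Part 1A about 0%.
- GM 10 h, CV 50% (σ = 0.472): Part 1B ln(1.15)/σ = 0.296, so 38%; Part 1A ln(2.35)/σ = 1.81, so 3.5%. The mean of retained half-lives is 7.8 h in Part 1B and 10.5 h in Part 1A, against a true mean of 11.2 h.

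**The case against.** A reader might infer that Part 1B sampling ends at 24 h and that every half-life above 11.5 h is necessarily lost. The documents do not support that for Cycle 1. Table 1-4 has the Day 8 pre-dose sample, and if it is quantifiable and used the ceiling is about 71.5 h. What remains is that the SAP does not place that sample in the first-dose profile. It describes draws outside the two profiles as sparse, and at its nominal 144 h the Day 8 draw falls outside the SAP's 156 to 180 h trough window. In Cycle 2 there is no such sample.

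Nor is AUC0-48 incalculable in Part 1B. The SAP permits interpolation or extrapolation, requires the extrapolated percentage to be listed, and removes AUCs more than 20% extrapolated, a limit that AUC0-48 reaches at about 12 h. It is also not one of the dose-proportionality parameters. Labelling would therefore serve as well as deletion.

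It is also tempting to blame the two-half-life rule alone for any bias in clearance. In the mono-exponential model, a first-dose profile ending at 24 h already fails the 20% rule above 10.3 h, so AUC0-inf, CL and VD are gone before 11.5 h. Restoring only those excluded solely by the two-half-life rule would change T1/2 and nothing else in that model.

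Finally, SAP 8.1 rules out formal comparison between parts, excluded values are flagged with reasons in listings, n is reported for each summary, and the planned population PK model works from concentrations, so these exclusions need not carry into it. All of that stands. It limits the harm to how the summaries are read, but it does not stop the Part 1B summaries from being truncated on the value they estimate.

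**Conclusion.** The point holds as a limitation of the Part 1B non-compartmental summaries. AUC0-48 is not observed beyond 24 h there, and both exclusion rules act at about half the Part 1A threshold: 11.5 h against 23.5 h for T1/2 after the first dose, 10.75 h against 22.75 h in Cycle 2 without the optional 1 h sample, and 10.3 h against 20.7 h for first-dose AUC0-inf and the CL and VD derived from it.

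The Cycle 1 ceilings assume that the Day 8 value is below quantification or unused. The T1/2 ceilings assume the earliest possible start of the terminal phase, and the 20% thresholds assume mono-exponential decline. The size of the bias cannot be fixed from the documents: it is negligible for half-lives around 6 h and material around 10 h with wide variability. These are expected proportions, not forecasts for a table: SAP Table 4 lists two Part 1B cohorts, and SAP Section 6 plans three to six DLT-evaluable patients per cohort. At six patients, 38% is about 2.3 and 11% about 0.7. A reader should not conclude that half-life or clearance will be biased, or that the SAP would declare an interaction. The documents support only that such a bias can arise, and that the planned summaries would not show its size.

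**What to change.** In SAP 8.6.1:

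1. Restrict AUC0-48 to Part 1A, or label it as estimated in Part 1B. Use AUC0-24, which is sampled to its end in both parts, wherever the parts are shown side by side.
2. Summarise T1/2, AUC0-inf, CL and VD with and without patients excluded by the two-half-life rule or the 20% extrapolation rule, and give the number excluded per part and per rule.
3. State whether the Day 8 pre-dose sample enters the Part 1B first-dose profile.

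The cost is SAP wording and one extra summary per parameter, with no new samples. The unrestricted summaries will include less precise values and should be labelled accordingly.

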#### **Pharmacokinetics**

Pharmacokinetics of BNT411 was evaluated across different animal species. No accumulation or sex-related differences in exposure were observed with weekly dosing in either rat or monkey. Exposure increases with dose showed a minor non-linearity which was more pronounced in rats than in cynomolgus monkeys.

*In vitro* plasma protein binding of BNT411 was similar across all tested species and was 64% for human plasma proteins.

*In vitro* studies on induction/inhibition of drug-metabolizing enzymes did not indicate potential interactions based on the low systemic exposure levels calculated for the proposed clinical dose levels. A study with human liver microsomes and recombinant CYP enzymes revealed that BNT411 was predominantly metabolized by CYP3A4 and CYP3A5.

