6 SAMPLE SIZE DETERMINATION

The sample size for Parts 1A and 1B is driven by the 3+3 trial design and will range from three to six DLT-evaluable patients per cohort, depending on the number of DLTs which may occur. In total, between 6 and 60 DLT-evaluable patients are planned to be enrolled in the Part 1A, and between 6 and 30 DLT-evaluable patients are planned to be enrolled in the Part 1B.

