- $AUC_{0-\infty}$: AUC from time 0 extrapolated to infinity, calculated as $AUC_{0-\infty} = AUC_{0-\text{last}} + C_{\text{last}}/\lambda_z$, where C_{last} is the last quantifiable (measurable) concentration.
- C_{max} : Maximum (peak) concentration.
- T_{max} : Time of maximum (peak) concentration.
- λ_z : terminal elimination rate constant.
- $T_{1/2}$: terminal elimination half-life computed as $(\ln 2)/\lambda_z$.
- CL: Clearance, calculated as Dose/ $AUC_{0-\infty}$. Dose will be converted, as necessary, to reflect the amount of anhydrous BNT411 administered (molecular weight 439.5579 g/mole).
- V_D : Volume of distribution, calculated as $[CL/\lambda_z]$.

The following PK parameters will be determined from plasma concentrations of BNT411 after the fourth dose on Cycle 2 Day 1 (or Cycle 2 Day 2 for Part B):

- AUC_{0-24} : partial AUC from time 0 to 24 hours calculated using the linear-log trapezoidal method.
- $AUC_{0-\text{last}}$: AUC from time 0 to the last measurable time-point calculated using the linear-log trapezoidal method.
- $AUC_{0-\tau}$: AUC from time 0 to the end of the 168-hour dosing interval (τ) calculated using the linear-log trapezoidal method.
- C_{max} : Maximum (peak) concentration.
- T_{max} : Time of maximum (peak) concentration.
- λ_z : Terminal elimination rate constant estimated by linear regression of log concentration vs. time; at least three data points are required to compute this parameter.
- $T_{1/2}$: Terminal elimination half-life computed as $(\ln 2)/\lambda_z$.
- CL: Clearance, calculated as Dose/ $AUC_{0-\tau}$. Dose will be converted, as necessary, to reflect the amount of anhydrous BNT411 administered (molecular weight 439.5579 g/mole).
- V_D : Volume of distribution, calculated as $[CL/\lambda_z]$.
- $R_{A,C_{\text{max}}}$: Accumulation ratio for C_{max} computed as C_{max} after Cycle 2 Day 1 (or Cycle 2 Day 2 for Part B) divided by C_{max} after Cycle 1 Day 1 (or Cycle 1 Day 2 for Part B).
- $R_{A,AUC}$: Accumulation ratio for AUC computed as AUC_{τ} after Cycle 2 Day 1 (or Cycle 2 Day 2 for Part B) divided by AUC_{τ} after Cycle 1 Day 1 (or Cycle 1 Day 2 for Part B).
- $T_{1/2,\text{eff}}$: Effective half-life for accumulation computed as $\ln(2)\tau/\ln(R_{A,AUC}/[R_{A,AUC}-1])$.

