All concentration values reported as no results (not collected or not determined) values will be treated as missing. For the calculation of concentration summaries, all concentrations below the quantifiable limit (BLQ) will be treated as 0. For the purpose of calculating PK parameters and plotting mean and individual concentration-time profiles, BLQ values will be treated as 0 prior to the first measurable concentration. After the first measurable concentration, subsequent BLQ values within the PK profile will be treated as missing. Descriptive statistics at any point will only be calculated if at least 2/3 of the individual data were measured and were quantifiable.

Dose-proportionality analysis:

The dose-proportionality of the PK parameters $AUC_{0-\text{last}}$, $AUC_{0-\text{inf}}$, and C_{\max} for the single-dose PK profile and $AUC_{0-\tau}$ and C_{\max} for the multiple-dose PK profile will be investigated over the administered dose range using the following power model,

$\ln(\text{parameter}) = a + b * \ln(\text{dose})$, where a is the intercept and b is the slope.

Dose proportionality will be assessed for Cycle 1 Day 1 (or Cycle 1 Day 2 for Part B) and Cycle 2 Day 1 (or Cycle 2 Day 2 for Part B) of the trial separately.

Each log-transformed PK parameter will be fit with a power model with a fixed effect term for log-transformed dose. For each PK parameter, the slope and associated 90% CI will be presented. Dose proportionality will be assessed based on whether the 90% CI includes 1.0.

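### The SAP has no rule for the effective half-life when the accumulation ratio is 1 or less, so its cohort summary would be biased upward if BNT411 accumulates little

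*SAP*

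**What the plan says.** SAP Section 8.6.1 derives two accumulation ratios after the Cycle 2 dose, one for Cmax and one for AUC. The AUC ratio is introduced by "Accumulation ratio for AUC computed as" the Cycle 2 AUC over the dosing interval divided by the Cycle 1 value. The interval is fixed: "AUC from time 0 to the end of the 168-hour dosing interval". The effective half-life is then obtained from that ratio ("Effective half-life for accumulation computed as" ln(2)τ/ln(R/[R−1])).

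The same section requires all PK parameters to be summarized by cohort. Terminal half-life and Tmax have their own lists of statistics. For the rest, "All other PK parameters will be summarized using n, arithmetic mean, SD, CV%, geometric mean, geometric CV%, median, minimum, and maximum". The effective half-life falls under this sentence; read instead as a kind of half-life, it would still get a mean and a median.

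The section has rules for large AUC extrapolation ("AUC and all related parameters (i.e., CL, V_D) will be presented but excluded from the calculation of summary statistics"), for a poorly estimated terminal slope, for outliers and for concentrations below the quantification limit. None covers an accumulation ratio of 1 or less. On expected accumulation, the protocol's non-clinical summary (Section 2.1.4.3) says: "No accumulation or sex-related differences in exposure were observed with weekly dosing in either rat or monkey".

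**The concern.** The ratio is observed, one per patient, and carries the error of two AUC estimates. If the drug does not accumulate over a week, about as many ratios fall below 1 as above it. Patients below 1 have no effective half-life and drop out. Patients above 1 stay in, and small excesses over 1 convert to long half-lives because the interval is 168 h. The values are therefore missing from one side only, and the cohort mean or median describes measurement noise. At stake is a PK table that could show an effective half-life of two to three and a half days beside a much shorter terminal half-life, with no explanation in the plan.

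**Working it through.** **Inputs.** From the SAP: the formula and τ = 168 h (8.6.1), and cohort size, which "will range from three to six DLT-evaluable patients per cohort" (Section 6). From the protocol: backfill to as many as 14 patients in a cohort (4.1.1.1) and the animal accumulation statement (2.1.4.3). Assumed, because neither document gives them: the true human half-life and the within-patient CV of AUC. The plan states no figure for this parameter, so there is none to reproduce.

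**Step 1: is the formula right?** At steady state R = 1/(1 − 2^(−τ/T)). Solving for T gives the SAP's expression. With τ = 168 h, half-lives of 4, 8, 12, 24, 36, 48 and 72 h are each recovered exactly.

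**Step 2: where does it have a value?** For R < 1 the argument R/(R−1) is negative and has no logarithm. At R = 1 there is a division by zero. Only R > 1 returns a number. Since ln(2) × 168 = 116.45 h, the result is 116.45/ln(R/(R−1)):

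| R | Effective half-life (h) |
|---|---|
| 1.001 | 16.9 |
| 1.01 | 25.2 |
| 1.05 | 38.2 |
| 1.10 | 48.6 |
| 1.20 | 65.0 |
| 1.30 | 79.4 |

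**Step 3: where would true R lie?** A half-life of 8 h gives R = 1.0000005, and 24 h gives 1.0079. Either is effectively 1 compared with the noise in an AUC ratio.

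**Step 4: what would be summarized?** Take observed R as true R times a lognormal error with log-scale SD s = √(2 ln(1 + CV²)), from two independent AUCs. With true R = 1, half the ratios are at or below 1, and the median of the remainder is the 75th percentile of all ratios, exp(0.6745 s). For CV 10%, s = 0.1411, so R = 1.0998 and the half-life is 116.45/ln(1.0998/0.0998) = 48.5 h. For CV 30%, s = 0.4152, so R = 1.3232 and the half-life is 82.6 h. Over true half-lives of 2 to 24 h:

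| CV | No value | Median of the rest (h) |
|---|---|---|
| 10% | 48–50% | 48–49 |
| 15% | 48–50% | 58 |
| 20% | 49–50% | 66–67 |
| 30% | 49–50% | 83 |

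Simulation with 400,000 draws per setting agrees. A twelve-fold change in true half-life moves the median by less than 1 h, whereas the CV moves it from 48 to 83 h.

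**Step 5: when does the bias fade?** At a true half-life of 72 h (R = 1.2475) and CV 5%, 0.1% of patients have no value and the median is 72 h, which is correct. At 72 h and CV 20%, 21% have no value and the median is 86 h. At 48 h and CV 20%, 37% have no value and the median is 73 h.

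**Step 6: cohort level.** With true R near 1, the chance that at least one patient has no value is 1 − 0.5³ = 0.88 for three patients and 1 − 0.5⁶ = 0.98 for six.

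**The case against.** The strongest reply is that little depends on this parameter, and most of that stands. The effective half-life is not in the objectives table or in the parameter list of protocol Section 8.9. The accumulation ratios are summarized in their own right, are defined at and below 1, and would show a value near 1. Terminal half-life is reported separately, population PK modelling is planned, and the reported n would reveal the lost patients. What n does not show is that the losses all come from one side.

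The SAP also has a two-thirds rule: "Descriptive statistics at any point will only be calculated if at least 2/3 of the individual data were measured and were quantifiable". It stands under non-quantifiable concentrations and is not written for an undefined derived parameter. If it were stretched to cover this one, with true R near 1 a summary would still appear with probability 0.50 (n = 3), 0.34 (n = 6) or 0.09 (n = 14).

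A reader might infer three stronger things, none of which the documents support:

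- **That the formula is wrong.** Step 1 shows that it is the exact inverse of the steady-state relation. What is missing is a handling rule.
- **That the table would mislead the dosing schedule.** Protocol Section 4.4 bases weekly dosing on the time needed to replenish plasmacytoid dendritic cells. Escalation follows DLT counts (4.1.1.1), the recommended dose is an integrated judgement (4.1.1.2), and no rule uses the effective half-life. The SAP also says that Part 2 no longer applies.
- **That a spurious value is certain.** The evidence for R near 1 is one statement about two animal species. Human accumulation is unknown, and Step 5 shows that the answer depends on it.

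**Conclusion.** The point holds in limited form. That the formula has no value for R of 1 or less is algebra, and that the SAP has no rule for the case is plain from Section 8.6.1. The upward bias depends on true accumulation being close to 1, which the animal data suggest but do not establish for patients. Under that condition and a half-life of 2 to 24 h, about half the patients have no value and the median of the others is about 48 to 83 h for a CV of 10% to 30%. Both ranges are assumptions. With a half-life of about 3 days and a small CV, the bias largely goes away. The damage is confined to one supplementary descriptive parameter: the accumulation ratios and terminal half-life are unaffected. It is still worth correcting before the tables are produced, because the SAP followed literally gives a selectively biased summary.

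**What to change.** In SAP Section 8.6.1, state that individual effective half-lives are listed and not summarized. Show patients with an AUC accumulation ratio of 1 or less as 'not calculable, no accumulation', and report their number. Derive any cohort-level or pooled value from the geometric mean ratio over all patients with both AUCs, and give that ratio's 90% CI. Report 'not estimable' unless the whole interval lies above 1; this covers cohorts where no interval can be computed, such as the single-patient cohorts. The simpler alternative is to delete the parameter and rely on the accumulation ratio.

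The change takes a few sentences in the SAP, with no new data and no protocol amendment. The price is that the effective half-life will often be reported as not estimable in cohorts of three to six. Some selection on chance remains, but it is small: if true R is 1, the lower limit of a two-sided 90% interval exceeds 1 in about 5% of cohorts.
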